4.1.3.2 Timepoint Windows

For tumour assessments:

- The protocol assigned windows for tumour assessments will be used to assign the result to a particular timepoint.
- Examples applicable to each module will be defined separately for that module.
 - Module 1: Section [4.2.3.2](#)

For safety assessments:

- Results will be presented as recorded in the database and no windowing to assign the result to a particular timepoint will be done.

4.1.3.3 Handling of Unscheduled Timepoints

Unscheduled timepoints will be included in listings but will not be included in by-timepoint summaries. Unscheduled timepoints have the potential to be included in summaries showing the maximum or minimum values while on IP.

4.1.3.4 Multiplicity/Multiple Comparisons

The handling of multiplicity/multiple comparisons is specific to each module and are discussed separately for each module.

- Module 1: Section [4.2.3.4](#)

4.1.3.5 Handling of Protocol Deviations in Study Analysis

Important protocol deviations (IPDs) are those deviations from the protocol likely to have an impact on the perceived efficacy and/or safety of study intervention.

The following general deviation categories will be defined. These deviations will be reviewed on a case-by-case basis by AstraZeneca to determine importance. Deviations considered to be important will be listed and discussed in the CSR as appropriate. All decisions on importance will be made ahead of database lock and will be documented prior to the primary analysis being performed.

- Patients who deviate from entry criteria per CSP

- No baseline Lugano assessments on or before the date of first dose
- Received prohibited concomitant medications or therapies
- Participants deviating from prescribed dosing regimen
- Missed timepoints, assessments, or treatments that, in the opinion of the investigator, were due to Coronavirus Disease 2019 (COVID-19) global pandemic, and where there was a significant effect on either completeness, accuracy and/or reliability of the participant's data, or the participant's rights, safety or wellbeing
- Missing scheduled efficacy assessments
- Deviation from Good Clinical Practice as determined by medical review (for example insufficient informed consent)

A detailed list of protocol deviations to be considered are defined in the study specific protocol deviation specifications.

Participants with no baseline Lugano assessments will be excluded from the response evaluable set. None of the other deviations defined in this study will lead to participants being excluded from any analysis populations described in this SAP. If a deviation is serious enough to have a potential impact on the primary analysis, sensitivity analyses may be performed. The need for such a sensitivity analysis will be determined following review of the protocol deviations ahead of database lock and will be documented prior to the analysis being conducted.

A list of all protocol deviations will be reviewed and decisions regarding how to handle these deviations in the analyses will be documented by the study team physician, medical scientist, clinical pharmacology scientist and statistician prior to database lock.

4.1.3.6 Missing Dates

Generally, the imputation of dates is used to decide if an observation is treatment emergent for AEs or concomitant medications. The imputed dates should not be used to calculate durations, where the results would be less accurate.

The following are the guidelines used when partial dates are detected in the study:

- For missing diagnostic dates (eg, disease diagnosis), if the day and/or month are missing use 01 and/or January. If year is missing, put the complete date to missing.
- For missing AE and concomitant medication start dates, the following is applied:
 - Missing day – impute the 1st of the month unless month is the same as month of the first dose of the study drug then impute first dose date.
 - Missing day and month – impute 1st January unless year is the same as first dose date then impute first dose date.

- Completely missing – impute first dose date unless the end date suggests it could have started prior to this in which case impute the 1st of January of the same year as the end date.
- Imputed start date should be no later than the end date.
- For missing AE and concomitant medication end dates, the following is applied:
 - Missing day – impute the last day of the month unless both the month and year are the same as the last dose date or the primary analysis date cut-off (DCO) date then impute the last dose date or the primary analysis DCO date.
 - Missing day and month – Impute 31st December unless the year is the same as the last dose date or the primary analysis DCO date then impute the last date or the primary analysis DCO date.
 - Completely Missing – before imputing a date, consider whether the AE/medication is still ongoing and also when it started in relation to study drug. If the ongoing flag is missing then assume that AE is still present/ medication is still being taken (ie, do not impute a date). If the AE/medication has stopped and start date is prior to first dose date, then impute first dose date. Or if it started on or after first dose date then impute a date that is after the last dose of study drug date.
- Flags will be retained in the database indicating where any programmatic imputation has been applied, and in such cases for AEs and concomitant medications, any durations will not be calculated.

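### The SAP's start-date imputation matches on month without year, so a day-missing AE or medication from the first-dose month of a later year is moved back to first dose

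*SAP*

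**What the plan says.** SAP section 4.1.3.6 (Missing Dates) sets the rules for partial dates. Their stated purpose is that "the imputation of dates is used to decide if an observation is treatment emergent for AEs or concomitant medications".

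- **Start date, day missing:** "impute the 1st of the month unless month is the same as month of the first dose of the study drug". Where the months agree, the start is set to the day of first dose. The year is not mentioned.
- **Start date, day and month missing:** "impute 1st January unless year is the same as first dose date then impute first dose date". The year is compared.
- **End date, day missing:** "impute the last day of the month unless both the month and year are the same as the last dose date" (or the data cut-off date). Month and year must both match.
- **Guard on start dates:** "Imputed start date should be no later than the end date".
- **Durations:** imputed dates are flagged and "in such cases for AEs and concomitant medications, any durations will not be calculated".

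Two later sections depend on these dates. SAP 5.6.2.1 defines the treatment-emergent phase as running from first administration to 30 days after last dose, and ending sooner if subsequent cancer therapy starts. SAP 5.1.8.1 classes medications as prior, concomitant or post-treatment from imputed start and stop dates.

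**The concern.** The day-missing start rule should fill in only the day. Because its exception depends on the month alone, it can also replace a year that the site did record. The neighbouring rules do compare the year, so the omission looks like a drafting slip. A programmer who follows the text will nevertheless code it as it stands.

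What is at stake is the classification of safety records. SAP 5.6.2.1 says the post-treatment phase is there to capture possible causally related SAEs. A late related SAE with a partial start date could be taken out of that phase and reported among treatment-emergent events, with onset on the day of first dose. Likewise, a medication begun after treatment ended could appear in the concomitant medication summary.

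**Working it through.** The plan states no figure for this point. The check applies the rule as written, and then with a year condition added, to test dates.

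**Inputs**

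- Rules as set out in SAP 4.1.3.6.
- Treatment-emergent phase: first dose to last dose + 30 days (SAP 5.6.2.1).
- AEs are collected from consent to 30 (± 7) days after last dose (protocol 8.3.1). Consent is at most 30 days before first dose (protocol Table 9, footnote b). In long-term and survival follow-up, only SAEs related to study drug or procedures are collected (protocol 8.2.2, 8.2.3).
- Assumed dates: first dose 15 March 2022; last dose 20 September 2022, or 20 June 2023 for a participant still on drug in March 2023.

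**Rule as written:** if the month equals the first-dose month, start = first-dose date; otherwise start = 1st of the recorded month.

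**Rule with year:** the same, but the exception needs month and year both to match.

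| Recorded start | Last dose | As written | With year | Effect |
|---|---|---|---|---|
| Mar 2022 | 20 Sep 2022 | 15 Mar 2022 | 15 Mar 2022 | None |
| Mar 2023 | 20 Sep 2022 | 15 Mar 2022, treatment-emergent | 1 Mar 2023, post-treatment | Class changes |
| Mar 2023 | 20 Jun 2023 | 15 Mar 2022, treatment-emergent | 1 Mar 2023, treatment-emergent | Onset date only |
| Apr 2023 | 20 Sep 2022 | 1 Apr 2023 | 1 Apr 2023 | None |
| Mar 2020, ongoing medication | 20 Sep 2022 | 15 Mar 2022, concomitant | 1 Mar 2020, concomitant | Start date only |
| Mar 2020, medication ended 10 May 2020 | 20 Sep 2022 | Blocked by the guard | 1 Mar 2020, prior | Class unchanged |

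**Row 2 in detail.** The treatment-emergent phase ends on 20 September + 30 days = 20 October 2022, well before March 2023. The shift is 365 − 14 = 351 days, because 15 March 2022 to 15 March 2023 is 365 days and 1 March is 14 days before that.

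**Does the guard help?** It is only an upper bound on the start. A record that began in a later year also ended after first dose, so setting its start to first dose never breaks the guard.

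**Can later-year records occur?** Yes. Treatment continues until progression (protocol 10.4.1), follow-up continues after it, and the final analysis takes in all data beyond the primary analysis (SAP 4.2.1). The Schedule of Activities also marks AE evaluation and concomitant medication at long-term follow-up. An affected record must start at least 365 − 30 = 335 days after first dose (first dose on the 31st, record on the 1st of the same month a year later).

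**Can earlier-year AEs occur?** No. The same arithmetic puts the nearest day of the same month a year earlier at least 335 days before first dose, while AE collection begins at most 30 days before it. A check of every first-dose date from 2021 to 2024 found no case.

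**The case against.** The best defence is that the month of first dose naturally means one particular month of one particular year. The rule fills a missing day, the list is introduced as guidelines, and overwriting a recorded year would not be imputation at all. That is probably what was intended. It does not settle the matter, because where this list wants both elements it says so: "unless both the month and year are the same as the last dose date". Read beside that, the start-date rule is month-only.

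The limits on impact stand. Scheduled AE collection stops about a month after last dose, so the AEs open to reclassification are mainly related SAEs from follow-up. Imputed dates are flagged and not used for durations.

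A reader might also infer two wider harms, and the documents support neither.

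- **Pre-treatment AEs becoming Day 1 treatment-emergent events.** The consent window rules out an AE from the first-dose month of an earlier year. Medical history does not fall under this rule. An AE starting before first dose in the same month and year is set to first dose with or without a year condition, so that outcome does not come from the missing year.
- **Prior medications becoming concomitant.** SAP 5.1.8.1 defines prior medications by stop date. If the medication stopped before first dose, it stays prior and the guard blocks the first-dose start. If it is ongoing, or stopped on or after first dose, it is concomitant under either start date. If it has stopped but the end date is wholly missing, the imputed end is first dose or later, so it is again concomitant either way.

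**Conclusion.** The start-date rule is wrong as written, with a narrow effect. It changes the class of a record only when four things coincide: the day is missing, the month is that of first dose, the year is later, and the record belongs after the treatment-emergent phase (for an AE) or after last dose (for a medication). An AE then becomes treatment-emergent and a medication concomitant. If the participant is still on drug, the class is right and only the onset date is wrong. For a medication begun in an earlier year and still in use, only the start date is wrong.

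The 351-day shift rests on the assumed dates. The documents give no count of partial dates, so the number of affected records cannot be estimated. It might be put at one in twelve of the day-missing dates from other years, but that assumes dates spread evenly over the months and includes earlier-year records whose class does not change. Nor is every shift a full year or more, as the 351 days show. Few records are likely. ORR, CR rate, DoR, PFS and OS do not use this rule. This is a minor correction to a safety derivation.

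**What to change.** In SAP 4.1.3.6, make the day-missing start-date exception depend on month and year together, as the end-date rule already does. For example: *if the day is missing, use the 1st of the recorded month; if the recorded month and year are both those of first dose, use the first-dose date.* Records from the same month and year as first dose are handled as before.

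The cost is one line of SAP text and a check that the AE and medication derivation code tests both elements. No new data are needed.

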4.1.3.7 Sample Size

Sample size is specific to each module and is discussed separately for each module.

- Module 1: Section [4.2.3.7](#)

4.2 Module 1

4.2.1 Timing of Analyses

The DCO for the primary analysis for each Module 1 PTCL cohort (Cohorts 1 and 2) will occur after 21 response-evaluable participants in the cohort have had the opportunity to be followed for at least 6 months since their first dose or have progressed or have initiated other anticancer therapy, or when 75% of participants have progressed or died, whichever occurs first. If one cohort reaches its planned primary analysis DCO ahead of the other, then the slower enrolling cohort may be evaluated for efficacy responses at the same time. The purpose of evaluating the slower cohort early would be for internal planning and to review continued development of the AZD4573 in one or both r/r PTCL groups. When both cohorts have reached their primary analysis DCOs the efficacy and safety data may be pooled for analysis. Additional data cuts may also be performed, if required.

The DCO for primary analysis of the Module 1 cHL Cohort (Cohort 3) will occur after 21 response-evaluable participants in the cohort have had the opportunity to be followed for at least 6 months since their first dose or have progressed or have initiated other anticancer therapy, or when 75% of participants have progressed or died, whichever occur first. Additional data cuts may also be performed, if required.

At the end of the module a final analysis will be conducted to incorporate all data (up to and beyond the primary analysis) from all participants.

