10.1.1 Schema

Figure 5 Module 1 Schema: AZD4573 Monotherapy in Participants with r/r PTCL and r/r HL

AZD4573 Monotherapy Treatment

^a Dosing regimen based on AZD4573 monotherapy RP2D in lymphoma = 12 mg weekly.

^b Dose confirmation in first 6 participants/cohorts (safety/PK/PD) → SRC. Additional dose levels may be explored depending on the emerging clinical data in PTCL/cHL.

^c Twenty-one participants per cohort, and **CCI**

CCI

^d Twenty-one participants per cohort, and **CCI**

CCI

^e Primary analysis at N = 21 for each cohort, with the primary analysis after approximately 6 months or when 75% of participants have progressed or died (Section 10.6). Additional data cuts may also be performed if required.

Abbreviations: AE, adverse event; ALCL, anaplastic large cell lymphoma; BV, brentuximab vedotin; cHL, classical Hodgkin Lymphoma; CR, complete response, CTCAE, Common Terminology Criteria for Adverse Events; CTCL, cutaneous T-cell lymphoma; DCO, data cut-off; ECG, electrocardiogram; ECOG, Eastern Cooperative Oncology Group; N, number; NK PTCL, natural killer/peripheral T-cell lymphoma; ORR, overall response rate; PD, pharmacodynamic; PR, partial response; PTCL, peripheral T-cell lymphoma; r/r, relapsed/refractory; RP2D, recommended phase II dose.

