10.8.1.2 Disease Assessment Schedule

Baseline tumour assessments will be performed using radiologic imaging by CT with contrast and PET-CT during the screening period. CT scans with contrast will cover neck, chest, abdomen, pelvis and any other disease sites; PET scans will cover the whole body from base of skull to mid-thigh.

Radiologic scans (ie, contrast CT) and PET scans will be performed as specified in [Table 15](#)

below, and thereafter to confirm CR or as clinically indicated. Unscheduled radiologic scans may be performed at investigator discretion if deemed clinically indicated.

Table 15 Radiologic Scans and PET Scans for Tumour Assessments

Timepoints		Required radiologic scans ^a	
Screening		Contrast CT	PET
During study ^b	After 8 weeks (~2 cycles)	Contrast CT	PET
	After 17 weeks (~5 cycles)	Contrast CT	
	After 26 weeks (~8 cycles)	Contrast CT	PET
	After 38 weeks (~12 cycles)	Contrast CT	
	After 50 weeks (~16 cycles)	Contrast CT	PET
	After 62 weeks (~20 cycles)	Contrast CT	
	After 74 weeks (~24 cycles)	Contrast CT	PET
	After 86 weeks (~28 cycles)	Contrast CT	
	After 98 weeks (~32 cycles)	Contrast CT	PET
	Every 12 weeks (~4 cycles) thereafter until the end of the study	Contrast CT	
Every 24 weeks (~8 cycles) thereafter until the end of the study		Contrast CT	PET
30-day follow-up visit ^c		Contrast CT	PET

^a Following complete metabolic response, subsequent scheduled PET assessments are no longer mandatory.

^b Window of \pm 1 week for all timepoints.

^c Tumour assessments will be repeated at this visit for discontinued participants if not previously performed within the required timeframe ie 9 weeks for participants that discontinued before Week 26, and 12 weeks for those that discontinued after Week 26.

If a PET-CT is not available, an independent PET and a diagnostic-quality CT scan (with contrast) can be used. If PET and CT scans are done on the same day, the PET must be performed prior to the contrast-enhanced CT not to compromise the PET read-out.

Post screening, the CT portion of a PET-CT (without contrast) may replace a contrast CT per local institutional practice; however, certain radiographic requirements are needed for acceptance, as described in the Site Radiology Manual, provided separately from this protocol.

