4.1.3.1 General Study Level Definitions

Baseline is the last non-missing value obtained prior to the first dose/administration of any IP and any information taken after first dose/administration of IP is regarded as post-baseline information. If 2 timepoints are equally eligible to assess participant status at baseline (eg, screening and baseline assessments both on the same date prior to first dose/administration

with no washout or other intervention in the screening period), the average is taken as the baseline value. For non-numeric laboratory tests (ie, some of the urinalysis parameters) where taking an average is not possible then the best value is taken as baseline as this is the most conservative. In the scenario where there are 2 assessments on Day 1 prior to first dose, one with time recorded and the other without time recorded, the one with time recorded is selected as baseline. Where safety data are summarised over time, study day is calculated in relation to date of first intervention of IP. For assessments on the day of first dose where time is not captured, a nominal pre-dose indicator, if available, serves as sufficient evidence that the assessment occurred prior to first dose. Assessments on the day of the first dose where neither time nor a nominal pre-dose indicator are captured is considered prior to the first dose. If no value exists before the first dose/administration, then the baseline value is treated as missing.

In all summaries, change from baseline variables will be calculated as the post-baseline value minus the value at baseline. The percentage change from baseline will be calculated as $(\text{post-baseline value} - \text{baseline value}) / \text{baseline value} \times 100$. For any endpoint subjected to log transformation, the change from baseline calculated and summarised on the log scale are back-transformed and presented as a ‘baseline scaled ratio’ (BSR). Percentage change is then calculated as $(\text{BSR} - 1) \times 100$.

Study Day 1 is defined as the date of the first dose of IP (Cycle 1 Day 1). For timepoints (or events) that occur on or after first dose of IP, Study Day is derived as $(\text{date of timepoint} [\text{event}] - \text{date of first dose of IP} + 1)$. For timepoints (or events) that occur prior to first dose, Study Day is defined as $(\text{date of timepoint} [\text{event}] - \text{day of first dose of IP})$. There is no Day 0 defined for this study.

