5.2.5.2 Derivations

OS (months) = (date of death or censoring – date of first dose + 1) / (365.25/12).

Any participant not known to have died at the time of analysis will be censored based on the last recorded date on which the participant was known to be alive. Participants known to be alive or dead after the DCO for analysis will be censored at the DCO. Participants lost to follow-up will be censored at the date the participant is last known to have been alive. At study closure, any participant still alive after last patient last visit for the study will be censored at the date of last patient last visit.

Note: Survival calls will be made in the week following the date of DCO for the analysis, and if participants are confirmed to be alive or if the death date is after the DCO date these participants will be censored at the date of DCO. The status of ongoing, withdrawn (from the study) and “lost to follow-up” participants at the time of the final OS analysis should be obtained by the site personnel by checking the participant’s notes, hospital records, contacting the participant’s general practitioner and checking publicly-available death registries. In the event that the participant has actively withdrawn consent to the processing of their personal data, the vital status of the participant can be obtained by site personnel from publicly available resources where it is possible to do so under applicable local laws.

Note: For any OS analysis performed in the absence of survival calls being made, it may be necessary to use all relevant eCRF fields to determine the last recorded date on which the participant was known to be alive for those participants still on intervention (since the SURVIVE module is only completed for participants off IP if a survival sweep is not performed). The last date for each individual participant is defined as the latest among the following dates recorded on the eCRFs:

- AE start, stop and change in severity dates
- Admission and discharge dates of hospitalization
- Study IP date
- End of IP date
- Concomitant medication start and stop dates
- Laboratory test dates
- Date of vital signs
- Disease assessment dates on eCRF
- Start and stop dates of alternative anticancer intervention
- Date last known alive on survival status eCRF
- End of study date

Duration of follow-up for OS is reported separately for censored participants and non-censored participants as well as combined for all participants and is defined as follows:

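### The primary data cut-off can fall at 6 months (about day 183) while the Week 26 CT and PET window stays open to day 189, so a compliant late scan can miss the primary analysis

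*SAP*

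**What the plan says.** SAP 4.2.1 gives two routes to the primary data cut-off in each cohort.

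- **Minimum follow-up.** 21 response-evaluable participants must "have had the opportunity to be followed for at least 6 months since their first dose", or have progressed or started other anticancer therapy.
- **Event share.** The alternative is "or when 75% of participants have progressed or died, whichever occurs first".

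The Protocol has the same rule in 1.1, 10.4.1 and 10.9.2. Footnote e to Figure 5 (10.1.1) puts it more loosely: "primary analysis after approximately 6 months or when 75% of participants have progressed or died".

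Table 15 in Protocol 10.8.1.2 sets the scans. Week 8 has contrast CT and PET, Week 17 has contrast CT only, and the row beginning "After 26 weeks (~8 cycles" has both again. The window is one week either side at every timepoint. SAP Appendix A gives the Week 26 window as days 175 to 189. Neither document links the cut-off to completion of the Week 26 scan or to the end of its window.

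**The concern.** The follow-up minimum ends in the middle of the Week 26 window. A participant who reaches six months on the day of the cut may still have a properly timed Week 26 scan to come, and that scan would not be in the primary analysis.

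What is at stake differs by endpoint.

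- **CR rate.** For a participant on the fixed schedule, Week 26 is the only scheduled on-study PET between Week 8 and the cut. A first CR, or an upgrade from PR to CR, that shows only on PET would be absent.
- **PFS and DoR.** SAP 5.2.4.2 censors event-free participants at their last evaluable assessment, and SAP 5.2.3.2 carries that date into DoR. A participant with a pending Week 26 scan is censored at about Week 17 despite six months on study. Protocol 10.9.2 names DoR in particular among the success considerations.
- **ORR.** The primary endpoint changes only if the response is first seen at the pending scan.

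Protocol 10.4.1 uses the primary analysis to decide whether expansion cohorts may be added.

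**Working it through.** **Inputs.** Scan weeks and the one-week window: Protocol Table 15. Day windows: SAP Appendix A. Month length of 365.25/12 days: SAP 5.2.4.2 and 5.2.5.2. Day 1 is the first dose: SAP 4.1.3.1. Cohort size of 21: SAP Table 3.

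**Step 1. Reproduce the SAP windows** as 7 × week ± 7 days.

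- Week 8: 56 ± 7 = 49 to 63.
- Week 17: 119 ± 7 = 112 to 126.
- Week 26: 182 ± 7 = 175 to 189.

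All three match Appendix A.

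**Step 2. Locate six months.** 6 × 365.25/12 = 182.6 days, so day 183 is the first whole day. A calendar six months runs from 181 to 184 days. The scan is therefore nominally due on or just before the six-month mark. Only the late part of its window follows: 189 − 183 = 6 days. That is days 184 to 189, or 6 of the 15 window days. If the window is counted in elapsed days, so that the first dose is day 0, it closes on study day 190 and 7 of the 15 days follow day 183.

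**Step 3. Who is exposed.** These are the last-dosed participant and anyone first dosed within about 6 days before. The documents give no accrual rate. If the other 20 are spread evenly over 6 months, 20/182.6 × 6 = 0.66, so about 1.7 participants in all. Over 24 months, 20/730.5 × 6 = 0.16, so about 1.2.

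**Step 4. Expected missed scans.** Assume a cut exactly at six months for the last participant, scan dates uniform over the 14-day span, and 2 to 3 participants dosed per month.

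- Last participant: (189 − 182.6)/14 = 6.4/14 = 0.457. Counting whole days gives 6/15 = 0.40.
- A participant dosed *u* days earlier: (6.4 − *u*)/14. Summed over *u* from 0 to 6.4 at *r* per day, this is *r* × 6.4²/(2 × 14) = 1.46 *r*.
- At 2 per month, *r* = 2/30.44 = 0.066, giving 0.10. At 3 per month, *r* = 0.099, giving 0.14.
- Total: 0.55 to 0.60 per cohort, before removing anyone who has already progressed.

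**Step 5. Effect of one participant.** 1/21 = 4.8 points. For example, 6/21 = 28.6% (exact 95% CI 11.3 to 52.2) against 7/21 = 33.3% (14.6 to 57.0).

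**Step 6. Censoring.** Nominal Week 26 minus nominal Week 17 is 182 − 119 = 63 days, so PFS is censored about 9 weeks earlier for each missed scan.

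**Step 7. The other route.** 0.75 × 21 = 15.75, so 16 events fire the 75% trigger. That leaves 21 − 16 = 5 event-free participants, none with a guaranteed Week 26 scan.

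**The case against.** The strongest reply is that this is a small tolerance gap in a descriptive study. Protocol 10.9.1 states no hypothesis, ORR is reported with 80% and 95% intervals, and one participant moves the estimate far less than the interval width. Six months is a minimum, so the cut may come later and the gap may never arise. Staggered entry makes follow-up unequal anyway, and a 27-week minimum would not change that. All of this stands. It limits the size of the problem without removing it.

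Four stronger readings are tempting, and the documents do not support them.

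- **That the cut can fall up to a week before the scan is due.** The due date is day 182, on or before six months. The week in question is the late half of the permitted window.
- **That Week 26 is the only PET after Week 8.** Table 15 also schedules PET at Weeks 50, 74 and 98 and at the 30-day follow-up visit, and it may be done to confirm CR or when clinically indicated. The statement holds only for scheduled on-study PET before the cut.
- **That late responses are lost.** SAP 4.2.1 provides a final analysis that takes in data after the primary cut, and allows additional cuts. The data are deferred.
- **That ORR depends on the Week 26 PET.** SAP 5.2.1.1 counts scheduled and unscheduled scans and needs no confirmation, and Table 14 defines CT-based response. Exposed participants still contribute their Week 8 PET and CT and their Week 17 CT.

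**Conclusion.** The gap is real and modest. Under the minimum-follow-up route, a protocol-compliant Week 26 scan on days 184 to 189 can miss the primary analysis, because the cut is tied to six months and not to the end of the scan window. CR rate, PFS and DoR are more exposed than ORR.

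The expected loss is about 0.6 scans per cohort. That figure rests on three assumptions found in neither document: a cut on the first permitted day, uniform scan timing, and accrual of 2 to 3 per month. It is an upper-end figure, since a later cut or earlier progression reduces it. The 4.8 points apply only when a missed scan would have changed that participant's response category, and the documents give no basis for that probability. The final analysis restores the data, but possibly after the expansion decision.

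The 75% trigger is a separate and potentially larger route to the same gap.

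**What to change.** In SAP 4.2.1, for all three cohorts, replace the six-month minimum with at least 27 weeks from first dose, described as the Week 26 assessment plus its one-week window. 27 × 7 = 189 days, which exceeds the longest calendar six months (184 days), so the Protocol's minimum is still met and the SAP can change first. Align Protocol 1.1, Figure 5 footnote e, 10.4.1 and 10.9.2 at the next amendment, since Protocol Appendix A 1 requires ethics and applicable regulatory approval of amendments.

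This does not cover a cut set by the 75% trigger. If that fires first, report with the primary results how many event-free participants still have a Week 26 assessment pending (up to 5 of 21).

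The cost is a wording change and a cut at most about one week later, with no new visits, scans or participants. It is a cheap improvement.
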